7.1 Procedure Schedules – Full Protocol

SCI and Controls – Complete protocol

PROCEDURE	7.2 INITIAL EVALUATION			7.3 AIM 1	7.4 AIM 2
	Visit #1 Functional Mapping	Visit #2 Range of Motion	Visit #3 Familiarization	Visit #4 TMS	Visit #5 StartReact
Kinematic recordings					
EMG recordings					
Transcutaneous SCS					
BoMI					
Motor tasks					
TMS					
StartReact					

7.2 Initial evaluation: Determine the effect of SCS on motor responses and range of motion

To determine an initial baseline for each participant, we will evaluate motor responses elicited by transcutaneous SCS in the initial evaluation phase. Participants will visit the lab for 1) a functional mapping where we measure spinal responses elicited by SCS, 2) a range of motion evaluation where we measure the range of motion on different joints with and without SCS, and 3) a familiarization phase where participants learn to control the body-machine interface using their leg movements supported by SCS.

Participants: 100 unimpaired participants and 12 participants with spinal cord injury (spinal cord injury level C4-T9) with motor impairments in the legs (complete ASIA A, or incomplete ASIA B, C, or D) and in the chronic stage of SCI (>6 months postinjury) will participate in this experiment, which will be submitted for review and approval to Washington University School of Medicine Institutional Review Board. Unimpaired participants will be recruited to perform either one of the five potential visits (Visits# 1-5) or all five visits. Approximately 16 unimpaired participants are expected to complete each type of protocol. SCI participants will be recruited for the five visits in total.

Experiments with unimpaired, control participants will be used to refine collection procedures and instruments and to prepare an improved, more refined research design that will ensure effective and high-quality data collection with SCI participants. Data collected on control subjects will also be used to establish baseline behavior for comparison of SCI participant task performance and may be used to generate generalizable knowledge.

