Average MEP and StartReact responses (of 20 responses) will be used to quantify changes in corticospinal and reticulospinal tract excitability¹⁵. A paired sample t-test of response amplitude and latency (time from stimulation to muscle response) will be used to test the hypothesis that BoMI training with SCS results in enhanced corticospinal tract excitability during precision-control movements and reticulospinal tract excitability during range-of-motion movements. In addition, a Student's *t*-test with a Holm-Sidak adjustment for multiple comparisons will be performed to compare the difference between changes in corticospinal excitability induced by the type of motor task (precision control vs. range-of-motion), joint (ankle vs. hip), and group (control vs. SCI).

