8.4 Sample Size

We plan to include in this study a total of 100 unimpaired and 12 SCI human volunteers over the course of two years. We expect that only 90% of unimpaired and 70% of SCI subjects initially recruited will conclude the experiment. Therefore, we will need to recruit 110 unimpaired and 16 SCI volunteers in order to reach the recruitment targets.

The number of subjects has been powered from the results of previous studies using similar methods to investigate structural changes in the brain after BoMI practice^{22,73}. Although the power is adequate, it might be possible that we are unable to detect significant changes in motor capacity. If no within-subject significant changes are found in preliminary experiments, we can extend the duration of training within one session, or extend the protocol to several sessions. If no significant group changes are found, we can recruit six more SCI participants for the study (a 50% increase).

9. Management of Intercurrent Events

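### Section 8.4 calls 100 unimpaired and 12 SCI participants the powered number, but the visit plan brings only about 32 controls (16 to 36 by reading) to either aim's test

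*Combined protocol and SAP*

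**What the plan says.** Section 8.4 (Sample Size) states: "We plan to include in this study a total of 100 unimpaired and 12 SCI human volunteers over the course of two years". On the basis of these numbers it says only: "The number of subjects has been powered from the results of previous studies using similar methods", the previous work being on structural brain changes following BoMI practice. It then adds: "Although the power is adequate, it might be possible that we are unable to detect significant changes in motor capacity". It gives no alpha, sidedness, power, effect size or standard deviation, and no number per analysis.

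The participants paragraph of Section 7.2 (Initial evaluation) sets the visit plan. For controls: "Unimpaired participants will be recruited to perform either one of the five potential visits (Visits# 1-5) or all five visits". And: "Approximately 16 unimpaired participants are expected to complete each type of protocol". For the injured group: "SCI participants will be recruited for the five visits in total".

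The schedule in Section 7.1 heads Visits 1 to 3 as initial evaluation (functional mapping, range of motion, familiarization), Visit 4 as TMS under Aim 1 and Visit 5 as StartReact under Aim 2.

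Section 8 (Data Analysis and Statistical Plan) tests only MEP and StartReact responses. The within-subject analysis reads: "A paired sample t-test of response amplitude and latency (time from stimulation to muscle response) will be used to test the hypothesis". A Student's t-test with Holm-Sidak adjustment then compares changes in corticospinal excitability by motor task, by joint and by group (control versus SCI).

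**The concern.** A sample size described as powered should be the number that enters the test it was powered for. Here the only control number given in Section 8.4 is 100, while the visit plan sends most controls to a single visit and three of the five visits carry no outcome that Section 8 tests. No control analysis in the plan can therefore be as large as the number beside which power is called adequate.

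What is at stake is how control results are read. If SCS shows no effect on MEPs or StartReact in controls, someone relying on Section 8.4 would judge that null against a sample of 100. The actual sample would be about a third of that and able to detect only a considerably larger effect. The hypotheses in Section 7 make this matter more, because they predict an effect for some task and muscle combinations and none for others. How much weight an absent effect can bear depends directly on the true number.

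**Working it through.** **The plan's own figure.** The powered number cannot be reproduced, because Section 8.4 gives none of the inputs. What can be checked is whether the visit plan agrees with 100 controls in total.

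- Types of control protocol: five single-visit types + one all-five type = 6.
- Total: 6 × 16 = 96, close to 100.
- In reverse: 100 / 6 = 16.7. Using Section 8.4's recruitment of 110 with 90% completing, 110 × 0.9 = 99 and 99 / 6 = 16.5. Both fit about 16.

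**Controls per analysis on this reading.**

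- Aim 1 (Visit 4): 16 Visit-4-only + 16 all-five = 32.
- Aim 2 (Visit 5): 16 Visit-5-only + 16 all-five = 32.
- Neither aim (Visit 1, 2 or 3 only): 3 × 16 = 48.
- With 15 to 16.7 per type, these become 30 to 33 per aim and 45 to 50 in neither.

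**Other readings.** The plan does not define a type of protocol.

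- 16 controls at each visit in all: 16 per aim.
- 16 for each single visit (5 × 16 = 80) and the remaining 100 − 80 = 20 doing all five: 16 + 20 = 36 per aim, 48 in neither.

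The range is thus 16 to 36 per aim. An aim could have 100 controls only if none did a different single visit, which the visit plan rules out.

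**SCI participants.** All 12 are planned for all five visits, so 12 is the planned number for both aims.

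**Detectable effects.** Assumptions, none taken from the documents: two-sided alpha 0.05, 80% power, no multiplicity adjustment. Power comes from the noncentral t distribution, and the equation is solved for the standardised effect d.

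- Paired test: df = n − 1, noncentrality = d × √n.
- Two-group test: df = n1 + n2 − 2, noncentrality = d / √(1/n1 + 1/n2).

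Paired test, controls only:

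- n = 100: d = 0.283
- n = 32: d = 0.511 (ratio 0.511 / 0.283 = 1.8)
- ends of the range: 0.749 at n = 16 and 0.480 at n = 36

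Paired test if the two groups were pooled (Section 8 does not say whether it is run by group):

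- n = 100 + 12 = 112: d = 0.27
- n = 32 + 12 = 44: d = 0.43 (ratio 0.43 / 0.27 = 1.6)

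Control versus 12 SCI:

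- 100 controls: d = 0.863
- 32 controls: d = 0.971 (ratio 0.971 / 0.863 = 1.13)
- ends of the range: 1.111 with 16 controls and 0.954 with 36

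Put as power: an effect that 100 controls would detect with 80% power is detected by 32 with about 34% power in the paired test. The corresponding figure for the comparison with 12 SCI is about 70%.

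**The case against.** The strongest reply is that nothing contradictory has been written. Section 8.4 speaks of the number of subjects; it names no test and never says that 100 controls enter one. Section 7 discloses the visit plan and the figure of about 16, and 6 × 16 agrees with 100 to the precision given. The cited studies cannot be consulted, so the powered quantity may have been something else, such as the 12 SCI participants. All of this stands: the total is not an arithmetic error, and n = 100 serves here as a benchmark, not as a test size that the plan claims. What remains is that Section 8.4 sets a claim of adequate power beside a control number that the design delivers to none of its tests.

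Three further points also stand and limit the concern.

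- The figures of 32 and 48 are inferred, not printed.
- The group comparison is limited mainly by the 12 SCI participants, so the number of controls changes it little.
- Section 8 names that comparison for corticospinal excitability only; no group test is specified for Aim 2.

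A reader might infer that the 48 or so controls outside both aims are wasted. The documents do not support this. Section 7.2 says that controls serve to refine procedures and instruments and to provide baseline behaviour for comparison with SCI task performance. A reader might also take the five visits in the synopsis, or the schedule's title covering both groups, to mean that every control attends all visits. The participants paragraph expressly says otherwise.

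**Conclusion.** The concern holds as a fault in the sample-size statement. On every reading of the visit plan set out above, no Section 8 test has 100 controls; the likely number is about 32 per aim, with a range of 16 to 36. That no test reaches 100 is firm. The exact split is only moderately certain, because it depends on what counts as a type of protocol.

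The size depends on the test. For a paired test in controls, the smallest detectable effect is about 1.8 times what 100 would give (0.51 against 0.28). If the groups are pooled it is about 1.6 times (0.43 against 0.27), and for control versus SCI about 1.13 times (0.97 against 0.86). All of these rest on the assumed alpha, power and absence of adjustment; applying Holm-Sidak to the group comparison would raise its detectable effects.

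It would go too far to conclude that the study is underpowered. With no target effect in the documents, adequacy can be neither confirmed nor refuted. Nor does the point touch the SCI within-subject test, whose planned 12 participants attend both aim visits.

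**What to change.** Restate Section 8.4 by planned test:

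- Within-subject paired test, Aim 1 and Aim 2: about 32 controls and 12 SCI each, saying whether the groups are tested separately or pooled.
- Group comparison of corticospinal excitability: about 32 controls against 12 SCI.
- Controls seen only at Visit 1, 2 or 3 (about 48): procedure refinement and baseline behaviour, not part of the powered number.

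Define a type of protocol in Section 7.2 so that these numbers can be read off; if the intended split differs, use the intended numbers. Replace the claim of adequate power with the detectable effect for each test at its own size, stating alpha, sidedness and power, and reflecting the Holm-Sidak adjustment where it applies.

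The cost is wording only, with no extra participants or visits. The downside for the sponsor is that the stated figures become less favourable.

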Study Title: Neural Facilitation of Movements in People With SCI
NCT number: NCT05354206
IRB ID #: 202111151 (The Washington University in St. Louis IRB)
PI: [name]
Document Type: Protocol
Document Date: 11/10/2022

Neural facilitation of stimulation-assisted movements in people with spinal cord injury

Principal Investigator:

[name]
Assistant Professor of Biomedical Engineering and Neurosurgery
Department of Biomedical Engineering
Washington University McKelvey School of Engineering
email: [contact]

Collaborators:

[name]
Instructor of Psychiatry
Department of Psychiatry
Washington University School of Medicine
email: [contact]

Study team members:

[name]
[name]
[name], OTD, OTR/L, ATP
[name]
[name], FNAI
[name]
[name]
[name], OTR/L, ATP
[name], PT, DPT, NCS

Version: November 10, 2022

Synopsis

Study title	Neural facilitation of stimulation-assisted movements in people with spinal cord injury
Objective	To understand the contribution of individual neural tracts to movements facilitated by transcutaneous spinal cord stimulation using transcranial magnetic stimulation, loud auditory stimuli, wearable sensors, motion tracking, and electromyography.
Hypothesis	Previous studies supported a potential role of spinal cord stimulation on the excitability of corticospinal and reticulospinal tract. We aim to identify the specific contributions of cortico- and reticulospinal networks towards reinforcing different types of movements enabled by transcutaneous spinal cord stimulation in unimpaired volunteers and volunteers with spinal cord injury. The results from this study may serve as preliminary data for the development of targeted rehabilitation strategies that take advantage of residual connections to maximize recovery after spinal cord injury.
Study period	Planned enrollment duration: approximately 12 months Planned study duration: 1-2 hours per subject, 5 visits
Number of subjects	112 (100 unimpaired, and 12 volunteers with spinal cord injury)
Study design	This study will measure changes in corticospinal and reticulospinal excitability associated with spinal cord stimulation during different leg movements.

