3.1 Rationale for this study

This 1-year study will provide the necessary data to prepare a clinical trial investigating whether activity-dependent reorganization of cortico- and reticulospinal circuits are primary contributors towards the long-lasting improvements in function that have been observed in humans. Moreover, we will study whether different types of training used in rehabilitation can be used to enhance the excitability of these neural structures and evaluate their role in the learning of skilled motor tasks²²⁻²⁵. An understanding of how we can accelerate plasticity through residual cortical and reticulospinal connections may enable the development of rehabilitation strategies that take advantage of patient-specific residual functions to further augment recovery.

4. Study Objectives

The goal of this project is to generate evidence-based knowledge of changes in the short-term excitability of corticospinal and reticulospinal neural structures that may mediate immediate improvements in motor function enabled by SCS.

Aim 1. Determine which kinds of SCS-facilitated movements are mediated by the corticospinal tract. I will use TMS to test whether SCS can enhance motor evoked potential (MEP) response time and amplitude as individuals use their legs to perform motor control tasks with different levels of dexterity.

Aim 2. Determine which kinds of SCS-facilitated movements are mediated by the reticulospinal tract. Using the same protocol, I will test whether SCS can enhance StartReact response time and amplitude.

5. Selection of Subjects – Inclusion/Exclusion Criteria

We plan to include in this study a total of 100 unimpaired and 12 SCI human volunteers over the course of one year.

Data collection will be performed at Washington University in St. Louis Danforth and Medical campus. Subjects will be referred by Drs. [name], [name], [name], [name], and [name], who are co-investigators on this project.

Approximately equal numbers of men and women will be recruited from all ethnic and racial groups. The racial composition of the population in St. Louis is approximately 44% Caucasian, 46% Black or African American, 4% Asian, 4% Hispanic, 2% Other. This will be the expected composition of our volunteer pool, of which the minority portion exceeds the national norm.

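### Section 8.4 allows the SCI group to grow from 12 to 18 after a non-significant group result, with no adjustment if the same endpoint is tested again

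*Combined protocol and SAP*

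**What the plan says.** Section 8.4 (Sample Size) plans 12 SCI participants and ends with a contingency: "If no significant group changes are found, we can recruit six more SCI participants for the study (a 50% increase"). The same paragraph describes the risk in terms of motor performance: "it might be possible that we are unable to detect significant changes in motor capacity". The sentence before the contingency deals separately with non-significant within-subject changes, and its remedy is more training rather than more participants.

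Section 8 (Data Analysis and Statistical Plan) names two kinds of test:

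- "A paired sample t-test of response amplitude and latency", for the hypothesis about BoMI training with SCS.
- An additional Student's t-test "with a Holm-Sidak adjustment for multiple comparisons will be performed to compare the difference between changes in corticospinal excitability", by type of motor task, joint, and group (control versus SCI).

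Neither section states a significance level or sidedness, when the check at 12 is made, or how the data from 18 are analysed.

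On controls, section 7.2 (Participants) has unimpaired volunteers attend either a single visit or all five: "Approximately 16 unimpaired participants are expected to complete each type of protocol".

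On purpose, the Synopsis says: "The results from this study may serve as preliminary data for the development of targeted rehabilitation strategies". Section 3.1 says: "This 1-year study will provide the necessary data to prepare a clinical trial".

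**The concern.** An extension triggered by a non-significant result gives the test a second chance to reach significance, but no second chance to lose it. If the enlarged sample is then tested at the unchanged level, the reported level understates the real false-positive rate. Holm-Sidak does not help, because it allows for several different comparisons and not for one comparison made twice on accumulating data.

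The effect depends on what a group change means. On the control-versus-SCI reading, an additional comparison is affected. On the reading of a group-level change within SCI, the test of the stated hypothesis is affected. In both cases a result that became significant only at 18 could be taken into the planning of the later clinical trial with more confidence than it deserves.

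**Working it through.** **The plan's own figure.** 6/12 = 50% and 12 + 6 = 18, so the stated increase reproduces.

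**Inputs from the documents.** SCI n = 12, then 18 (section 8.4). Controls with TMS data follow from section 7.2. There are six types of participation (five single visits, or all five), and 6 × 16 = 96, close to the planned 100. The TMS visit is attended by about 16 single-visit controls and about 16 five-visit controls. That gives 16 + 16 = 32, or 16 if only one of these sets is used.

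**Assumptions.** Two-sided 0.05; the same test at both looks; the extension always used after a non-significant first look; all 18 pooled; the same controls at both looks; normal data with equal variances.

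**Formula.** Overall rate = α + P(not significant at 12 and significant at 18). With no true effect, the two test statistics have correlation

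- paired, within SCI: √(12/18) = 0.816
- control versus SCI with m controls: √[(1/18 + 1/m)/(1/12 + 1/m)] = 0.900 for m = 16 and 0.870 for m = 32

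The bivariate normal approximation gives 7.7% (paired), 7.0% (m = 16) and 7.3% (m = 32). Simulation with the actual t-tests (1,000,000 null trials per case, Monte Carlo standard error about 0.0003) gives:

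| Test | Both looks at 0.05 | Both looks at 0.01 | Both looks at 0.10 | Both looks at 0.030 | Equal level that holds 0.05 |
|---|---|---|---|---|---|
| Control vs SCI, 16 controls | 7.1% | 1.5% | 13.7% | 4.4% | 0.034 |
| Control vs SCI, 32 controls | 7.3% | 1.6% | 14.1% | 4.5% | 0.033 (0.0336 before rounding down) |
| Paired, within SCI | 7.8% | 1.7% | 15.0% | 4.8% | 0.031 |

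**Extension used half the time.** The excess over 5% is halved. For the paired test, 5.0% + ½ × (7.8% − 5.0%) = 6.4%. For control versus SCI the result is 6.1% to 6.2%.

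**Trigger is a different outcome.** Suppose the extension follows a non-significant result on another outcome and the endpoint is tested once, at the final sample size. The paired test then has a rate of 5.0% if the two outcomes are uncorrelated, and about 5.1% to 5.2% at an assumed correlation of 0.5.

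**Power at 0.030 per look.** Take an effect that gives 80% power at n = 12 and 0.05. First-look power becomes about 73% (control versus SCI) or 72% (paired). If the extension is used when needed, two-look power is about 85% to 87% (16 to 32 controls) or 92% (paired).

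**The case against.** The strongest reply is that the inflation is conditional. Section 8.4 speaks of motor capacity while section 8 tests excitability, so the trigger may not be the tested endpoint at all. The text also does not say that the 18 are pooled and retested. This stands. A reader might infer that the error rate is inflated however the sentence is read, and the documents do not support that: with a different trigger and a single test, the rate stays at or close to 5%.

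Second, *group changes* is arguably clear. Section 8 uses the word group for control versus SCI, and section 8.4 has just dealt with within-subject change separately. This largely stands: control versus SCI is the more natural reading. The wording does not settle it, so the paired figure remains a possibility and not the main result.

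Third, the extension is optional, and section 9.3 describes the study as observational with no treatment tested. That lowers the stakes. It does not remove the problem, because an optional rule leaves the choice open after the result is known, and using it half the time still gives more than 6%.

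**Conclusion.** The concern holds in a limited form, and its severity is minor. If the trigger is the tested endpoint and all 18 are pooled and retested at an assumed two-sided 0.05, the per-test false-positive rate is about 7.1% to 7.3% for control versus SCI and about 7.8% for a paired test within SCI. The rate falls with less frequent use of the extension. It is essentially nominal if the trigger is another outcome and the endpoint is tested once.

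Two further inferences go too far. One is to compare the SCI group with all 100 controls, which gives a slightly higher rate; section 7.2 points to about 16 to 32 controls with TMS data. The other is to claim a familywise error rate. Section 8 does not fix the number of tests, and it attaches Holm-Sidak only to the additional t-test, not to the paired tests of amplitude and latency.

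**What to change.** Rewrite the contingency in section 8.4 as one paragraph. Name the outcome and the test that trigger the extension, and state alpha and sidedness. Then choose one option.

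1. **Two pre-specified looks at that test, at 12 and 18 SCI participants, each at an adjusted level.** To hold 0.05 for that single test, use about 0.033 (32 controls) to 0.034 (16 controls) for control versus SCI, about 0.031 for a paired test, or 0.030 if one value is to serve for either. Where section 8 applies Holm-Sidak, use the adjusted level as the family level in place of 0.05. Make no familywise claim for the paired tests. The cost is first-look power: about 72% to 73% at 0.030, against 80% at 0.05.

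2. **Label any result obtained after the extension as exploratory, and report the result at 12 beside it.** This costs no power and suits a study meant to yield preliminary data.

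Neither option requires new data collection or prevents the extension.
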